16.2 DERIVED VARIABLES

The efficacy variables are derived as follows:

- MADRS total score is the sum of the 10 items from the MADRS. If more than 2 items of the MADRS are missing, the total score will be set to missing
- *Responder on MADRS* is defined as a participant with $\geq 50\%$ reduction from baseline MADRS total score

- *Responder on CGI-S* is defined as participant achieving a score of ≤ 2 on the CGI-S of Illness scale.
- *Remitter on MADRS* is defined as a participant with MADRS total score ≤ 10
- BPRS+ total score is defined as the sum of 4 positive individual scores including suspiciousness, unusual thought content, hallucinations, and conceptual disorganization. If more than 1 item is missing, then the total score will be set to missing
- CADSS total score is defined as the sum of scores for 23 subjective items. If more than 4 items are missing, then the total score will be set to missing.

The total score at a particular visit will be calculated using $(\text{sum of nonmissing items}) \times (\text{total number of items}) / (\text{number of nonmissing items})$ only if the number of missing items is less than the specified number for each variable. Otherwise, the total score will be set to missing.

16.3 REPEATED OR UNSCHEDULED ASSESSMENTS OF SAFETY PARAMETERS

If a participant has repeated assessments before the start of the first treatment, the results from the final nonmissing assessment made prior to the start of the study treatment will be used as baseline. If end of double-blind treatment period assessments are repeated or if unscheduled visits occur during the double-blind treatment period, the last nonmissing postbaseline assessment will be used as the end of double-blind treatment period assessment for generating summary statistics. However, all postbaseline assessments will be used for PCS value determinations, and all assessments will be presented in the data listings.

16.4 MISSING DATE OF THE LAST DOSE OF STUDY TREATMENT

When the date of the last dose of study treatment is missing for a participant in the Safety Population, all efforts should be made to obtain the date from the Investigator. If after all efforts are made it is still missing, the last available dosing record date will be used as the last dose date.

16.5 MISSING SEVERITY ASSESSMENT FOR ADVERSE EVENTS

If severity is missing for an AE that started before the date of the first dose of study treatment, an intensity of mild will be assigned. If severity is missing for an AE that started on or after the date of the first dose of study treatment, an intensity of severe will be assigned. The imputed values for severity assessment will be used for the incidence summary; the values will be shown as missing in the data listings.

16.6 MISSING CAUSAL RELATIONSHIP TO STUDY DRUG FOR ADVERSE EVENTS

If the causal relationship to the study treatment is missing for an AE that started on or after the date of the first dose of study treatment, a causality of yes will be assigned. The imputed values for causal relationship to study treatment will be used for the incidence summary; the values will be shown as missing in the data listings.

16.7 MISSING DATE INFORMATION FOR ADVERSE EVENTS

The following imputation rules only apply to cases in which the start date for AEs is incomplete (ie, partly missing).

Missing month and day

- If the year of the incomplete start date is the same as the year of the first dose of study treatment, the month and day of the first dose of study treatment will be assigned to the missing fields
- If the year of the incomplete start date is before the year of the first dose of study treatment, *December 31* will be assigned to the missing fields
- If the year of the incomplete start date is after the year of the first dose of study treatment, *January 1* will be assigned to the missing fields

Missing month only

- If only the month is missing, the day will be treated as missing and both the month and the day will be replaced according to the above procedure

Missing day only

- If the month and year of the incomplete start date are the same as the month and year of the first dose of study treatment, the day of the first dose of study treatment will be assigned to the missing day
- If either the year of the incomplete start date is before the year of the date of the first dose of study treatment or if both years are the same but the month of the incomplete start date is before the month of the date of the first dose of study treatment, the last day of the month will be assigned to the missing day
- If either the year of the incomplete start date is after the year of the date of the first dose of study treatment or if both years are the same but the month of the incomplete start date is after the month of the date of the first dose of study treatment, the first day of the month will be assigned to the missing day

If the stop date is complete and the imputed start date as above is after the stop date, the start date will be imputed by the stop date.

If the start date is completely missing and the stop date is complete, the following algorithm will be used to impute the start date:

- If the stop date is after the date of the first dose of study treatment, the date of the first dose of study treatment will be assigned to the missing start date
- If the stop date is before the date of the first dose of study treatment, the stop date will be assigned to the missing start date

Table 16-2 **Imputation Scenarios**

Scenario	Complete			Imputable
	Year	Month	Day	
1	Yes	Yes	Yes	Complete
2	Yes	Yes	—	Yes
3	Yes	—	Yes	No ¹
4	Yes	—	—	Yes
5	—	Yes	Yes	No ¹
6	—	Yes	—	No ¹
7	—	—	Yes	No ¹
8	—	—	—	Yes

¹ Not allowed per database design

16.8 MISSING DATE INFORMATION FOR PRIOR OR CONCOMITANT MEDICATIONS

For prior or concomitant medications, including rescue medications, incomplete (ie, partly missing) start dates and/or stop dates will be imputed. When the start date and the stop date are both incomplete for a participant, the start date will be imputed first.

16.8.1 Incomplete Start Date

The following rules will be applied to impute the missing numeric fields for an incomplete prior or concomitant medication start date. If the stop date is complete (or imputed) and the imputed start date is after the stop date, the start date will be imputed using the stop date.

Missing month and day

- If the year of the incomplete start date is the same as the year of the first dose of study treatment, the month and day of the first dose of study treatment will be assigned to the missing fields

- If the year of the incomplete start date is before the year of the first dose of study treatment, *December 31* will be assigned to the missing fields
- If the year of the incomplete start date is after the year of the first dose of study treatment, *January 1* will be assigned to the missing fields

Missing month only

- If only the month is missing, the day will be treated as missing and both the month and the day will be replaced according to the above procedure

Missing day only

- If the month and year of the incomplete start date are the same as the month and year of the first dose of study treatment, the day of the first dose of study treatment will be assigned to the missing day
- If either the year of the incomplete start date is before the year of the date of the first dose of study treatment or if both years are the same but the month of the incomplete start date is before the month of the date of the first dose of study treatment, the last day of the month will be assigned to the missing day.
- If either the year of the incomplete start date is after the year of the date of the first dose of study treatment or if both years are the same but the month of the incomplete start date is after the month of the date of the first dose of study treatment, the first day of the month will be assigned to the missing day

16.8.2 Incomplete Stop Date

The following rules will be applied to impute the missing numeric fields for an incomplete prior or concomitant medication stop date. If the imputed stop date is before the start date (imputed or nonimputed start date), the imputed stop date will be equal to the start date.

Missing month and day

- If the year of the incomplete stop date is the same as the year of the last dose of study treatment, the month and day of the last dose of study treatment will be assigned to the missing fields
- If the year of the incomplete stop date is before the year of the last dose of study treatment, *December 31* will be assigned to the missing fields
- If the year of the incomplete stop date is after the year of the last dose of study treatment, *January 1* will be assigned to the missing fields

Missing month only

- If only the month is missing, the day will be treated as missing and both the month and the day will be replaced according to the above procedure

Missing day only

- If the month and year of the incomplete stop date are the same as the month and year of the last dose of study treatment, the day of the last dose of study treatment will be assigned to the missing day
- If either the year of the incomplete stop date is before the year of the date of the last dose of study treatment or if both years are the same but the month of the incomplete stop date is before the month of the date of the last dose of study treatment, the last day of the month will be assigned to the missing day
- If either the year of the incomplete stop date is after the year of the date of the last dose of study treatment or if both years are the same but the month of the incomplete stop date is after the month of the date of the last dose of study treatment, the first day of the month will be assigned to the missing day

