8.0 DEMOGRAPHICS AND OTHER BASELINE CHARACTERISTICS

Demographic parameters (age; age group (<20, 20-29, 30-39, 40-49, 50-59, and >=60); race; ethnicity; sex), baseline characteristics (weight; height; and body mass index, calculated as weight [kg]/(height [m])² will be summarized descriptively by treatment group for the Safety and mITT populations. Continuous variables will be summarized by number of participants and mean, SD, median, Q1 (25 percentile), Q3 (75 percentile), minimum, and maximum values. Categorical variables will be summarized by number and percentage of participants.

Abnormalities in participants' medical and surgical histories will be coded using the *Medical Dictionary for Regulatory Activities* (MedDRA), version 22.0. The number and percentage of participants with abnormalities in medical and surgical histories in each system organ class and preferred term will be summarized by treatment group for the Safety Population.

Prior medication is defined as any medication taken before the date of the first dose of study treatment. *Concomitant medication* is defined as any medication taken on or after the date of the first dose of study treatment.

Both prior and concomitant medications will be coded by drug name and therapeutic class. The use of prior and concomitant medications will be summarized by the number and percentage of participants in each treatment group for the Safety Population. If a participant took a specific medication multiple times or took multiple medications within a specific therapeutic class, that participant would be counted only once for the coded drug name or therapeutic class.

Formulations (including salts, esters, etc) containing the same active ingredient will be pooled under the coded drug name of the base compound. Medications containing multiple active ingredients of different coded drug names will be reviewed during the course of the study and may be pooled under a single coded drug name for analyses.

The number and percentage of participants taking each antidepressant therapy (ADT) and the number of ADTs (0, 1, 2, and >2) received in current episodes of major depressive disorder prior to randomization will be summarized by treatment group for the Safety Population. ADT medication selection criteria is included in [Table 8-1](#).

Table 8-1 Criteria for ADT medication

ADT Class	Medication List
Atypical	BUPROPION
	MIRTAZAPINE
	VILAZODONE and/or VILAZODONE HYDROCHLORIDE

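### When a medication's start and stop dates are both partial, SAP 16.8.1 and 16.8.2 conflict, and the stated order can turn a drug stopped before the study into a concomitant-only drug

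*SAP*

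**What the plan says.** SAP 16.8 sets the order: "When the start date and the stop date are both incomplete for a participant, the start date will be imputed first".

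SAP 16.8.1 covers the start. If only the year is known and it is the first-dose year, "the month and day of the first dose of study treatment will be assigned to the missing fields". A year-only start in an earlier year goes to 31 December of that year, and a start in a known earlier month goes to the last day of that month. The section also has a guard, with this condition: "If the stop date is complete (or imputed) and the imputed start date is after the stop date". When it is met, the start moves back to the stop.

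SAP 16.8.2 covers the stop. A stop with a known month earlier than the last-dose month goes to the last day of that month. Its guard applies when the imputed stop is "before the start date (imputed or nonimputed start date), the imputed stop date will be equal to the start date".

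SAP 8.0 then classifies each drug. Prior medication "is defined as any medication taken before the date of the first dose of study treatment"; concomitant medication is anything taken on or after that date. The same section counts the antidepressant therapies (ADTs) "received in current episodes of major depressive disorder prior to randomization will be summarized by treatment group". Protocol 7.7.1 lists antidepressants among the drugs to be discontinued before baseline and not used during the study.

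**The concern.** Both guards repair the same fault, a start that falls after its stop, but they move opposite dates. Where both dates have been imputed, both guards apply and the SAP names no winner. Two programmers could each follow the text and put the same antidepressant in different tables.

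The only hint of precedence is the instruction to impute the start first. At that moment no imputed stop exists, so the 16.8.1 guard has nothing to compare with. The stop is imputed next and the 16.8.2 guard then acts. An assumed start therefore overrides a stop month that was actually recorded.

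For an antidepressant, the by-arm concomitant table would show a prohibited drug on Day 1 that the record says had already stopped, and the prior-medication table would lose it.

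**Working it through.** The plan gives no figure to reproduce, so the rules were applied literally to example records. The first dose (15 May 2019) and last dose (29 May 2019, Day 15) are assumed, because the documents hold no participant dates.

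**The conflict, step by step: start 2019, stop March 2019**

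1. Start: year only, same year as the first dose, so 15 May 2019 (16.8.1).
2. Stop: March precedes the last-dose month, so 31 March 2019 (16.8.2).
3. The stop (31 March) is before the start (15 May).
4. 16.8.2 guard: stop becomes 15 May. The drug runs 15 May to 15 May, concomitant only.
5. 16.8.1 guard: start becomes 31 March. The drug runs 31 March to 31 March, prior only.

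**Which records are affected**

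| Start recorded | Stop recorded | 16.8.2 guard prevails | 16.8.1 guard prevails |
|---|---|---|---|
| 2019 | 15 March 2019 (complete) | 15 March to 15 March: prior | same |
| 2019 | March 2019 | 15 May to 15 May: **concomitant only** | 31 March to 31 March: prior |
| February 2019 | March 2019 | 28 February to 31 March: prior | same |
| 2018 | March 2019 | 31 December 2018 to 31 March 2019: prior | same |
| 2018 | June 2018 | 31 December to 31 December 2018: prior | 30 June to 30 June 2018: prior |
| 2019 | 2019 | 15 May to 29 May: concomitant only | same |

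Only the second row is misclassified by the guard. In the fifth row the guard moves the stop but the class does not change. The last row comes from the same-year rules; no guard acts, and the record does not rule out use on treatment.

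**Size, within the triggering date pattern only**

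A simulation drew 20,000 records per date pattern. All were truly stopped before first dose. First doses were spread evenly over 240 days from 1 March 2019, starts over the preceding 539 days (about the 18-month episode limit in Protocol 6.1), and stops between start and first dose.

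- Either date complete: 0% misclassified.
- Year-only start with a month-and-year stop: 33.4% if 16.8.2 prevails, 8.8% if 16.8.1 prevails. The guard accounts for 33.4 − 8.8 = 24.6%.

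The result depends strongly on the assumed first-dose date. With starts uniform over 548 days, the concomitant-only share of such records is 13.3% for a first dose in mid-March and 63.6% in mid-December. In 49% and 83% of these, respectively, the recorded stop month is before the first-dose month, which is the part caused by the guard: 0.133 × 0.49 = 6.5% and 0.636 × 0.83 = 53%. These are shares of records with this exact date pattern, not of all medications.

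**Effect on a table:** with about 25 participants per arm (SAP 14.0), one participant is 1/25 = 4 percentage points.

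**The case against.** The strongest defence is that 16.8.1 already covers the case. Its guard refers to a stop that is complete or imputed. If the guard is run once the stop has been imputed, the example is classified correctly; reading the order so that it never meets an imputed stop leaves that wording idle when both dates are partial. This stands as a fair alternative reading, so the concomitant-only result is not certain. But 16.8.2 expressly includes an imputed start, and nothing says that 16.8.1 is run again. The defence shows that the SAP can be read two ways, which is the point.

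A reader might infer that any partial start is sent to the first dose and any earlier stop dragged after it, so that past antidepressants are widely reported as on-treatment use. The documents do not support this. A complete stop is never moved, and starts in an earlier year or a known earlier month stay before the first dose. Older drugs of the episode more often began in an earlier year, which makes the triggering pattern less likely for them.

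A reader might also infer that the MADRS comparison is compromised. The models in SAP 10.1 and 10.2 contain no medication variable. Nor does SAP 8.0 say that the ADT count is built from imputed dates, and the schedule of activities lists prior medication history at Screening separately from concomitant medications.

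**Conclusion.** The point holds in a narrow form. When both dates are partial, the two guards contradict each other, and the stated order favours the one that can override a recorded pre-study stop month. A wrong class requires all of these: a start known only to the year, that year being the first-dose year, a partial stop whose recorded month precedes the first dose, and the 16.8.2 guard acting last.

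The consequence is limited to the descriptive prior and concomitant medication tables and, if it uses imputed dates, the count of current-episode ADTs before randomization. How many records qualify cannot be learned from the documents. The 24.6% figure, and the 6.5% to 53% range around it, rest on assumed uniform dates and describe only the triggering pattern. Severity is minor.

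**What to change.** In SAP 16.8.2, set an imputed stop equal to the start only when the start date is complete. When both dates are imputed and the start falls after the stop, set the start to the imputed stop, so that the 16.8.1 guard prevails. A stop whose recorded month or year is before the first dose is then never moved to or past the first dose.

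The cost is a sentence or two in the SAP and a small programming change, with no new data. There is one side effect to allow for. With the last dose on 29 May 2019, a drug recorded as starting in June 2019 and stopping in 2019 has an imputed start of 1 June and an imputed stop of 29 May. The changed rule would pull the start back to 29 May, out of its recorded month. It is concomitant either way, and limiting the change to year-only starts avoids the problem.

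Imputing every partial start to the earliest possible date is not recommended. It would make some drugs begun on treatment look prior, and a record with only 2019 for both dates would still show use during treatment.

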16.9 CHARACTER VALUES OF CLINICAL LABORATORY PARAMETERS

If the reported value of a clinical laboratory parameter cannot be used in a statistical summary table because, for example, a character string is reported for a parameter of the numeric type, a coded value must be appropriately determined for use in the statistical analyses. The actual values, however, as reported in the database will be presented in the data listings.

[Table 16-3](#) shows examples of how some possible laboratory results should be coded for the analysis.

Table 16-3 Examples of Coding Speci al Character Values for Clinical Laboratory Parameters

Laboratory Test	Possible Laboratory Results (in SI Units)	Coded Value for Analysis
Chemistry: ALT	< 5	5
Chemistry: AST	< 5	5
Chemistry: bilirubin, total	< 2	2
Urinalysis: ketones	> 0	Positive
	≤ 0, Negative	Negative
Urinalysis: pH	> 8.0, ≥ 8.0	8.0
	≥ 8.5	8.5
Urinalysis: glucose	≤ 50	0
	(50, 100]	1+
	(100, 250]	2+
	(250, 500]	3+
	(500, 1000]	4+
	≥ 1000	5+
Urinalysis: protein	≤ 15	0
	(15, 30]	1+
	(30, 100]	2+
	(100, 500]	3+
	≥ 500	4+

ALT = alanine aminotransferase; AST = aspartate aminotransferase; SI = *Le Système International d'Unités* (International System of Units).

17.0

CHANGES TO ANALYSES SPECIFIED IN PROTOCOL

None

18.0 **REFERENCES**

DOCUMENT HISTORY PAGE

Effect Date	Revision Number	Primary Author	Description of Change
